**IIS PROTOCOL SYNOPSIS**

**Protocol Title:** Fycompa titration intervals and effects on retention rates

**Principal Investigator Name:** [name]

**Principal Investigator Contact Information:** [name]  
[contact] [contact]  
[[contact]](mailto:[contact])

**Institution Name(s):** Banner University Medicine Neuroscience Institute

**Sub-Investigator Name, if applicable:** [name]  
[name]

**Do you plan on using other Institutions or centers to conduct study?**  YES  NO

**If yes, please list name(s) and address(es):** N/A

**Rationale:** With its novel mechanism of AMPA receptor blockade, Fycompa is efficacious for seizure reduction in both partial onset seizures and generalized tonic-clonic seizures. As only a few of antiepileptic medications have this capability, it is important to elucidate the ideal methods of avoiding complications and improving retention rates.

Recent studies find real-world rates currently range from 44-89% (Trinka et al 2016). Personal clinical experience has revealed difficulty in maintaining patients on Fycompa due to adverse effects. However, certain studies find correlations between slower titration schedules and lower side effect percentages (Trinka et al 2016, Lawthom et al, 2014).

We therefore propose to test whether a slower initial upward titration (2mg increase every 3 weeks) improves 1-year retention rates as compared to those of a more typical titration every 2 weeks. As any retention rate may be affected by adverse effects and/or seizure frequency, these will be followed as secondary endpoints.

**Study Design:** A total of 60 patients with a confirmed diagnosis of either partial onset or primary generalized epilepsy will be recruited into the trial. 30 patients will initiate Fycompa at a dose of 2 mg/day and titrate upward every 2 weeks to a target dose of 6 mg/day. Patients in this group will be designated Group A. The remaining 30 patients will also begin Fycompa at a dose of 2 mg/day but will titrate upwards every 3 weeks to a target dose of 6 mg/day and will be designated Group B. Initial study visits will occur every two weeks for the first 2 months in order to assess for titration related adverse effects. Long term evaluation of retention rates will be calculated at 3, 6, 9 and 12 months after enrollment.

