**Secondary:**

1. To compare the adverse effects reported in patients up-titrating Fycompa at a slower titration rate (Group B) to those titrating at a more conventional rate (Group A).
2. To evaluate the short term and long term efficacy of perampanel between the two treatment groups.

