## IIS PROTOCOL SYNOPSIS

- Other Therapy:** Concomitant antiepileptic and medical treatment will be allowed as deemed necessary by the Principle investigator and/or sub-investigators. .
- Efficacy Measures:** Patient diaries containing seizure types and frequencies along with adverse effects experienced will be maintained. Seizure diaries will be reviewed in Epilepsy Clinic during study visits occurring at the following intervals: weeks 0, 2, 4, 6, 8 then months 3, 6, 9, and 12. Data point collation at study visits will include:
1. Fycompa dose taken and duration at this dose
  2. Adverse effects experienced
  3. Alterations to Fycompa dose once in maintenance phase.
  4. Interim seizure types and number of each
  5. Interim changes in other medication during maintenance phase.
- Safety Measures:** Adverse effects and seizure frequency will be assessed at each clinic visit along with vital sign measurements and brief neurological exams. Dosage adjustments of the Fycompa and other concomitant medications will be done at the discretion of the Investigator during the maintenance phase.
- Correlative Science:** Data collected will be based on the patient's seizure/adverse effect diary as well as patient/caregiver reports at each study visit.
- Statistical Analysis:** The study will target a total size of 60 patients (30 per group). This sample size will allow for a power of 0.85 to determine significant difference of 30% retention in group A and 70% retention in group B.
- Primary endpoint will be Fycompa retention rate at the end of 1 year with Kaplan-Meier survival curves created for both groups. Log rank testing will be done to determine significant difference ( $p < 0.05$ ). Cox proportional hazard test will be done to quantify the odds of retention in each arm.
- Secondary endpoint analysis will be done to tabulated side effects experienced in each group and the percentages of patients reporting the effects. Seizure frequency per 28 days during initial titration and final maintenance will be calculated for each group. Comparison within groups will be made by ANOVA.
- Data Collection:** Data will be collected at each study visit through patient interview and the use of a seizure/adverse effect diary.

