**Study Drug Regimens:**

Group A will have Fycompa 2mg qD for 2 weeks, then 4mg qD for 2 weeks, then 6mg qD for at least 2 weeks. Further adjustments upward or downward in the maintenance phase will be allowed as per Investigator's discretion. We anticipate 15 will continue at 6mg, 8 will decrease to 4mg, and 7 will increase to 8mg during the next 46 weeks of maintenance.

Group B will have Fycompa 2mg qD for 3 weeks, then 4mg qD for 3 weeks, then 6mg qD for at least 3 weeks. Further adjustments upward or downward in the maintenance phase will be allowed as per the Investigator's discretion. We anticipate 15 will continue at 6mg, 8 will decrease to 4mg, and 7 will increase to 8mg for the remaining 40 weeks of maintenance.

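### One shared visit calendar fits Group A's titration but not Group B's, so the adverse-effect comparison mixes titration rate with unequal clinic observation on 6 mg (minor)

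*Combined protocol and SAP*

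**What the plan says.** The Study Design paragraph gives the early visits a specific purpose: "Initial study visits will occur every two weeks for the first 2 months in order to assess for titration related adverse effects". Efficacy Measures lists a single calendar, "weeks 0, 2, 4, 6, 8 then months 3, 6, 9, and 12", and describes no visits particular to either group.

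Study Drug Regimens sets the two schedules: "Group A will have Fycompa 2mg qD for 2 weeks, then 4mg qD for 2 weeks, then 6mg qD for at least 2 weeks", and "Group B will have Fycompa 2mg qD for 3 weeks, then 4mg qD for 3 weeks, then 6mg qD for at least 3 weeks". It then expects that in Group A "7 will increase to 8mg during the next 46 weeks of maintenance", and in Group B that "7 will increase to 8mg for the remaining 40 weeks of maintenance".

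Safety Measures places changes of dose in one phase: "Dosage adjustments of the Fycompa and other concomitant medications will be done at the discretion of the Investigator during the maintenance phase". The same section has adverse effects assessed at every clinic visit, and Efficacy Measures has patients keep a diary of them that is reviewed at visits.

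Secondary objective 1 is a between-group comparison: "To compare the adverse effects reported in patients up-titrating Fycompa at a slower titration rate (Group B) to those titrating at a more conventional rate". For it, Statistical Analysis plans a tabulation of side effects and the percentage of patients reporting each. It states no time window and no alignment to dose.

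**The concern.** Titration interval is the only planned difference between the groups. On this calendar it also changes how closely patients are observed in clinic once they reach 6 mg. The visits coincide with Group A's milestones, whereas the two-weekly series ends one week before Group B completes its stated minimum regimen.

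Two things could be affected. A percentage of patients reporting an effect depends partly on the opportunity to report it. Fewer early clinic assessments on 6 mg in Group B could lower its percentages, which is the direction the trial hopes to see. Separately, the plan speaks of dose adjustment only in the maintenance phase, and Group B's first scheduled visit in that phase comes much later than Group A's. If that mattered for retention, it would probably work against Group B.

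**Working it through.** **Inputs.** Visits at weeks 0, 2, 4, 6, 8 and months 3, 6, 9, 12 (Efficacy Measures). Dose periods of 2 + 2 + at least 2 weeks in Group A and 3 + 3 + at least 3 weeks in Group B; maintenance of 46 and 40 weeks (Study Drug Regimens). Assumptions: 12 months = 52 weeks, so month 3 is 52 / 4 = week 13, and a visit on the day of a dose step counts towards the dose just completed.

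**Step 1: the plan's own durations.** Group A: 2 + 2 + 2 = 6 weeks, and 6 + 46 = 52, which agrees with 12 months of follow-up. Group B: 3 + 3 + 3 = 9 weeks, and 9 + 40 = 49, which is 52 − 49 = 3 weeks short. Counting back from the end of the year instead, Group B's maintenance would begin at 52 − 40 = week 12. The documents therefore support two starting points for Group B, week 9 or week 12.

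**Step 2: milestones against visits.**

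| Milestone | Group A | Visit? | Group B | Visit? |
|---|---|---|---|---|
| Step to 4 mg | week 2 | yes | week 3 | no |
| Step to 6 mg | week 4 | yes | week 6 | yes |
| End of minimum time on 6 mg | week 6 | yes | week 9 | no |

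**Step 3: observation on 6 mg by week 8.** Group A: 8 − 4 = 4 weeks, with visits at weeks 6 and 8 (2 visits). Group B: 8 − 6 = 2 weeks, with a visit at week 8 (1 visit). Up to month 12 the visits after reaching 6 mg number 6 in Group A and 5 in Group B.

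**Step 4: first scheduled visit in the maintenance phase.** Group A: week 6, which is 6 − 4 = 2 weeks after reaching 6 mg. Group B: both possible starts (week 9 or 12) come after the week 8 visit, so the first is month 3, which is 13 − 6 = 7 weeks after reaching 6 mg. That is 13 − 9 = 4 weeks, or 13 − 12 = 1 week, into maintenance, depending on which start is meant.

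**Step 5: where the calendar is balanced, or favours Group B.** Each group has 9 scheduled visits in all. Both of Group B's increases (weeks 3 and 6) fall before week 8. Each group is seen 2 weeks after reaching 6 mg (A at week 6, B at week 8). Between the step to 4 mg and the step to 6 mg, Group A has 1 visit (week 4) and Group B has 2 (weeks 4 and 6).

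**Step 6: can the existing visits support equal windows?** Take the first 2 weeks on each of 2, 4 and 6 mg.

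- Group A: weeks 0–2, 2–4 and 4–6; the first visit at or after each window closes is week 2, 4 and 6.
- Group B: weeks 0–2, 3–5 and 6–8; the corresponding visits are weeks 2, 6 and 8.

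Every window is followed by a visit within 1 week (6 − 5 = 1 at most), so the comparison needs no change to the calendar.

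**The case against.** A common calendar is a defensible design. Identical visits from week 0 give both groups the same number of chances to report, and shorter time on 6 mg by week 8 in Group B follows directly from the schedules being compared. No passage promises a visit at each step or at the end of each regimen. Adverse effects are kept in a diary between visits, and the analysis has no week 8 cut-off, so effects in Group B between week 8 and month 3 can be recovered at month 3. All of this stands, and it limits the point to clinic observation at the target dose.

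Three stronger readings are tempting, and the documents do not support them:

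- **Group B's titration goes unmonitored.** Both increases lie inside the two-weekly window, and Group B is seen more often than Group A on 4 mg.
- **Group B's adverse-effect percentages will be biased downwards.** This is possible in direction, but the diary offsets it to an unknown extent and nothing in the documents lets its size be computed.
- **Group B's retention is harmed because adjustment must wait until month 3.** The plan leaves adjustment to the investigator within the maintenance phase and does not confine it to scheduled visits. If maintenance starts at week 12, month 3 follows only about a week later.

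What the objection leaves standing is that unaligned percentages cannot separate titration rate from unequal observation on 6 mg, and that the start of Group B's maintenance phase is inconsistent.

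**Conclusion.** The point holds and is minor. On the documents' own dates the shared calendar matches all three of Group A's milestones and one of Group B's three. By week 8 the difference on 6 mg is 4 weeks and 2 visits against 2 weeks and 1 visit. The first scheduled maintenance visit comes 2 weeks after reaching 6 mg in Group A and about 7 weeks after in Group B.

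This rests on month 3 being about week 13 and on patients moving at the stated minimum durations. The ordering for Group B is the same whether maintenance starts at week 9 or week 12. Neither the size of any bias in the adverse-effect comparison nor any effect on retention can be calculated from the documents.

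**What to change.** 1. **Add an aligned comparison to Statistical Analysis.** Keep the planned percentages over the common calendar period. Beside them, compare adverse effects over equal time since each dose step, for example the first 2 weeks on 2, 4 and 6 mg, using diary onset dates and the dose and duration already recorded at visits. Report how many patients in each group reached each step. The documents do not say whether diary entries are dated, so state that onset dates will be recorded. Cost: one supplementary table. Its limitation is that each row covers only patients who reached that dose, so it supplements the comparison of everyone randomised and does not replace it.

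2. **Reconcile Study Design, Efficacy Measures, Safety Measures and Study Drug Regimens** on when Group B's maintenance phase begins relative to the visits, including why 9 + 40 = 49 weeks when Group A's 6 + 46 = 52 fits the 12-month follow-up. Cost: a wording change.

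3. **An option for the sponsor to weigh** is moving the week 8 visit to week 9 in both groups. It would give Group B a visit at the end of its stated minimum period without adding a visit. It would also delay Group B's first visit on 6 mg from 2 to 3 weeks after the step (9 − 6 = 3), lengthen the gap between Group A's last two early visits to 3 weeks, and leave the visits after the step to 6 mg at 2 against 1. Items 1 and 2 do not depend on it.

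No dose or clinical rule is proposed.

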**Objectives:****Primary:**

To evaluate the differences in retention rate between patients using a more conventional upward titration schedule (Group A) vs. those using a slower up-titration schedule (Group B).

**Secondary:**

1. To compare the adverse effects reported in patients up-titrating Fycompa at a slower titration rate (Group B) to those titrating at a more conventional rate (Group A).
2. To evaluate the short term and long term efficacy of perampanel between the two treatment groups.

**Subjects and Centers:**

A total of 60 epilepsy patients will be recruited from the Epilepsy Center at Banner University Medicine Neuroscience Institute. 30 patients will be randomly assigned to treatment group A, up-titrating Fycompa every 2 weeks while the remaining 30 being assigned to group B, up-titrating Fycompa every 3 weeks.

**Inclusion Criteria:**

1. Must provide written informed consent signed by the subject or legal guardian prior to entering the study in accordance with the ICH, GCP guidelines if the written informed consent is provided by the legal guardian because the subject is unable to do so, a written or verbal assent from the subject must also be obtained.
2. Subject has a confirmed diagnosis of medically refractory epilepsy with or without secondary generalization for at least 12 months prior to visit 1.
3. Subjects currently being treated with 1 to 3 antiepileptic medications with or without VNS (does not count as an AED).
4. Subjects aged 18 to 75.
5. Subject's requiring an additional epilepsy medication due to either uncontrolled seizure and/or lack of tolerability with current epilepsy medications
6. Can be safely treated, in the opinion of the investigator with Fycompa.
7. Able and agrees to follow specified titration schedule
8. Subjects or a legal guardian who is able to communicate effectively with study personnel and considered reliable, able, willing and cooperative with regard to complying with protocol-defined requirements, including completion of the study diary.

**Exclusion Criteria:**

1. Any history of non-epileptic or psychogenic seizures.
2. Women who are currently pregnant, lactating or have plans to become pregnant in the immediate future.
3. Subjects with active suicidal ideation or behavior as evidenced by positive answers on the Columbia Suicide Severity Rating Scale (C-SSRS) or subject's with a history of suicidal ideation or attempt within 12 months.
4. Subjects with a suicidal attempt in the 12 months prior to Visit 1
5. Any clinically significant medical or psychiatric illness, psychological or behavioral problems, which in the opinion of the investigator would interfere with the subject's ability to participate in the study.
6. Subjects with severe hepatic impairment or severe renal impairment or on hemodialysis.
7. Any use of concomitant medication as listed in the drug insert, including medications known to be inducers of cytochrome P450 (CYP3A).

## IIS PROTOCOL SYNOPSIS

- Other Therapy:** Concomitant antiepileptic and medical treatment will be allowed as deemed necessary by the Principle investigator and/or sub-investigators. .
- Efficacy Measures:** Patient diaries containing seizure types and frequencies along with adverse effects experienced will be maintained. Seizure diaries will be reviewed in Epilepsy Clinic during study visits occurring at the following intervals: weeks 0, 2, 4, 6, 8 then months 3, 6, 9, and 12. Data point collation at study visits will include:
1. Fycompa dose taken and duration at this dose
  2. Adverse effects experienced
  3. Alterations to Fycompa dose once in maintenance phase.
  4. Interim seizure types and number of each
  5. Interim changes in other medication during maintenance phase.
- Safety Measures:** Adverse effects and seizure frequency will be assessed at each clinic visit along with vital sign measurements and brief neurological exams. Dosage adjustments of the Fycompa and other concomitant medications will be done at the discretion of the Investigator during the maintenance phase.
- Correlative Science:** Data collected will be based on the patient's seizure/adverse effect diary as well as patient/caregiver reports at each study visit.
- Statistical Analysis:** The study will target a total size of 60 patients (30 per group). This sample size will allow for a power of 0.85 to determine significant difference of 30% retention in group A and 70% retention in group B.
- Primary endpoint will be Fycompa retention rate at the end of 1 year with Kaplan-Meier survival curves created for both groups. Log rank testing will be done to determine significant difference ( $p < 0.05$ ). Cox proportional hazard test will be done to quantify the odds of retention in each arm.
- Secondary endpoint analysis will be done to tabulated side effects experienced in each group and the percentages of patients reporting the effects. Seizure frequency per 28 days during initial titration and final maintenance will be calculated for each group. Comparison within groups will be made by ANOVA.
- Data Collection:** Data will be collected at each study visit through patient interview and the use of a seizure/adverse effect diary.

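### The plan schedules no adverse-effect check after the increase to 8 mg it forecasts for 14 of 60 patients, and its side-effect table mixes that step with the randomised titration

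*Combined protocol and SAP*

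**What the plan says.** All references are to the synopsis in the combined protocol and SAP.

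- **Study Design** gives the reason for the early visits: "Initial study visits will occur every two weeks for the first 2 months in order to assess for titration related adverse effects".
- **Efficacy Measures** has diaries reviewed at visits in "weeks 0, 2, 4, 6, 8 then months 3, 6, 9, and 12".
- **Safety Measures** ties safety review to those visits: "Adverse effects and seizure frequency will be assessed at each clinic visit along with vital sign measurements and brief neurological exams".
- **Study Drug Regimens** fixes the 2, 4 and 6 mg steps for at least 6 weeks in Group A and at least 9 weeks in Group B. It then leaves further changes to the investigator. The forecast for Group A is that "7 will increase to 8mg during the next 46 weeks of maintenance", and for Group B that "7 will increase to 8mg for the remaining 40 weeks of maintenance". No dose above 8 mg is named anywhere.
- **Statistical Analysis** tabulates side effects by group, with the percentage of patients reporting each. It does not split them by phase or dose.
- **Secondary objective 1** is to compare adverse effects between the slower and the conventional titration rate.

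No section links a visit, contact or other assessment to a dose increase made during maintenance.

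**The concern.** The plan's reason for close early visits is that dose steps bring adverse effects. The move from 6 to 8 mg is also a dose step, and the plan expects it in nearly a quarter of its patients, yet the closely spaced visits end at week 8. If tolerability problems follow that step, the plan does not say when anyone will look for them. The Rationale reports difficulty keeping patients on the drug because of adverse effects, and retention is the primary endpoint, so this matters beyond the safety tables.

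There is also a question of interpretation. Secondary objective 1 asks about titration speed. Patients are randomised to an interval for the 2-to-6 mg steps only, and the later step is chosen patient by patient. A single 12-month count per group cannot show which effects belong to the randomised schedule.

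**Working it through.** **1. How many patients.** The forecast split per group (Study Drug Regimens) is 15 staying at 6 mg, 8 going down to 4 mg and 7 going up to 8 mg. 15 + 8 + 7 = 30, which matches the group size. Increases: 7 + 7 = 14, and 14/60 = 23.3%.

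**2. Visit gaps.** Taking one month as 365.25/12/7 = 4.35 weeks, visits fall at weeks 0, 2, 4, 6, 8, 13.0, 26.1, 39.1 and 52.2. Successive gaps are 2, 2, 2, 2, 5.0, 13.0, 13.0 and 13.0 weeks.

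**3. When maintenance can start.** Group A: 2 + 2 + 2 = week 6 at the earliest. Group B: 3 + 3 + 3 = week 9 at the earliest, after the last two-weekly visit.

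**4. Wait from an increase to the next scheduled visit.**

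| Increase made | Next visit | Wait |
|---|---|---|
| Group A, week 6 (earliest) | week 8 | 2 weeks |
| Group A, week 8 | month 3 | 13.0 − 8 = 5.0 weeks |
| Group B, week 9 (earliest) | month 3 | 13.0 − 9 = 4.0 weeks |
| Either group, at the month 3, 6 or 9 visit | next quarterly visit | 13.0 weeks |

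An increase made between two quarterly visits waits less than 13 weeks.

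**5. What pooling does to the table.** Let p_A and p_B be the proportions reporting an effect during the assigned titration. Suppose a further share q of those who had not reported it do so after the increase, with the same q in both groups. The pooled difference is

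[p_A + (1 − p_A)q] − [p_B + (1 − p_B)q] = (p_A − p_B)(1 − q).

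If increases are unrelated to earlier reporting, q is at most 7/30 = 0.233, reached only if every increased patient reports the effect. The difference then shrinks by at most 23%. If instead all 7 increases per group go to patients who had not reported the effect, and all 7 then report it, each proportion rises by 7/30. The difference is unchanged and the ratio moves towards 1. Either way the contrast is weakened or left alone, not reversed. The documents give no adverse-effect rates, so these are bounds under stated assumptions and not estimates.

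**6. Whether the data allow a split.** The items collected at visits include dose, time at that dose, adverse effects experienced and dose changes in maintenance. An onset date for each adverse effect is not named, and without one an effect cannot be placed before or after an increase.

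**The case against.** The best defence is that thinning visits after titration is an ordinary design choice. Study Design speaks of initial visits, and maintenance is a separate phase under the investigator's judgement. The document is a synopsis that neither describes nor forbids unscheduled contact, and the site runs weekly epilepsy clinics. The 14 is a forecast and 13 weeks is the worst case; some early increases would be seen within 2 to 5 weeks. Counting all effects by assigned group is also a legitimate comparison of two strategies. All of this stands, and it limits the point to a gap in what the plan specifies. It does not close the gap: informal contact is neither required nor standardised across groups, and diaries are reviewed at visits.

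A reader might go further and infer that the adverse-effect comparison is biased between groups, because Group A can be increased at the week 6 or 8 visit and seen 2 to 5 weeks later, while Group B's first scheduled visit after its minimum schedule is month 3, with the next about 13 weeks on. The documents do not support this:

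- Increases are not confined to scheduled visits, and a Group B increase at week 9 is seen about 4 weeks later.
- From month 3 the gaps are the same in both groups.
- The diary runs between visits, so a recorded effect counts whenever it is reviewed.
- The forecast number of increases is 7 in each group.

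Nor do the documents support reading 13 weeks as the usual wait, or saying that the 8 mg step always gets the least monitoring.

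**Conclusion.** The point holds as an omission with two consequences. First, on the plan's own forecast 14 of 60 patients (23%) have a dose increase to which no scheduled assessment is attached, and the wait for the next one can be as long as about 13 weeks. Second, the side-effect table mixes effects of a discretionary step with those of the randomised titration, which dilutes secondary objective 1. On the assumptions in the working, the difference shrinks by at most 23%, or stays the same while the ratio moves towards 1.

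This rests on the forecast applying to all 60 patients (dropout would lower the 14), on a month of 4.35 weeks, and on no follow-up arrangement existing outside the document. Whether a longer wait changes the reported percentages is not established. The point is worth correcting because the correction is cheap; it does not undermine the primary analysis.

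**What to change.** 1. Reconcile Study Design, Efficacy Measures and Safety Measures with Study Drug Regimens, so that the plan states how adverse effects are assessed after an increase made in maintenance, in the same way for both groups. The form and timing are for the sponsor and investigator to decide, and nothing here bears on whether or when a dose is increased. Moving the early visits to match Group B's 2-to-6 mg steps would not by itself settle this.
2. Add the onset date of each adverse effect to the existing diary.
3. Keep the 12-month side-effect table by assigned group. Add a second tabulation by group over one common calendar window from randomisation, fixed in advance. A common window is needed because the assigned schedules differ in minimum length (6 v 9 weeks), so counting each group over its own schedule would give unequal observation time. It should be long enough to contain Group B's 9 weeks.
4. In both tables, flag effects that began after an increase above 6 mg and show them on a separate line by group. The flag is needed in the common window too, since Group A can be increased from week 6. Report that line descriptively only, because patients who are increased are selected.

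Cost: a short amendment, one diary field, one extra tabulation with a split, and a small amount of follow-up work for existing staff (about 14 increases on the plan's forecast). No additional patients are needed.

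### No pre-treatment seizure window is defined and only a within-group comparison of two on-drug periods is planned, so change from pre-treatment cannot be estimated and the between-group efficacy objective has no matching analysis.

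*Combined protocol and SAP*

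**What the plan says.** Secondary objective 2 reads "To evaluate the short term and long term efficacy of perampanel between the two treatment groups".

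The analysis that would serve it is in the Statistical Analysis section of the synopsis: "Seizure frequency per 28 days during initial titration and final maintenance will be calculated for each group". The next sentence is "Comparison within groups will be made by ANOVA". No other test of seizure frequency is named.

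The Study Drug Regimens section shows that drug starts with the first titration step in both arms: "Group A will have Fycompa 2mg qD for 2 weeks, then 4mg qD for 2 weeks, then 6mg qD for at least 2 weeks", and "Group B will have Fycompa 2mg qD for 3 weeks, then 4mg qD for 3 weeks, then 6mg qD for at least 3 weeks".

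Under Efficacy Measures, diaries are reviewed at "study visits occurring at the following intervals: weeks 0, 2, 4, 6, 8 then months 3, 6, 9, and 12", and the seizure item collected is the count of each type in the interim. Safety Measures adds that seizure frequency is assessed at every clinic visit. No section describes a run-in, a look-back window or a minimum seizure count for entry. Inclusion criterion 2 requires medically refractory epilepsy for at least 12 months, and criterion 5 reads "Subject's requiring an additional epilepsy medication due to either uncontrolled seizure and/or lack of tolerability with current epilepsy medications".

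**The concern.** The meaning of a within-group comparison depends on its reference period. Here that period is initial titration, when patients are already taking Fycompa. The ANOVA therefore describes the change from early to later dosing. It does not describe a reduction from the patient's untreated rate, and with no untreated arm nothing else in the plan supplies one.

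The titration rate cannot stand in for a baseline either. It is measured after randomisation and under the schedule being compared, so subtracting it or adjusting for it could remove part of any difference between the schedules.

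Objective 2 is a contrast between groups. Two separate within-group results do not test that contrast, even if one is significant and the other is not. Followed as written, the plan would report an efficacy result that answers neither how far seizures fell from their pre-treatment level nor whether the two schedules differ.

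**Working it through.** **The plan's own figure.** The only power statement is 0.85 for 30% v 70% retention with 30 per group. It concerns the primary endpoint. By the Freedman log-rank formula:

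- hazard ratio = ln(0.70)/ln(0.30) = 0.296
- expected events = 30 × 0.70 + 30 × 0.30 = 21 + 9 = 30
- power = Φ(√30 × (1 − 0.296)/(1 + 0.296) − 1.96) = 0.845

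The figure reproduces. It says nothing about seizure frequency, but its retention rates are used below.

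**Are both analysed periods on drug?** Yes. Titration begins with the first 2 mg dose, and maintenance follows it. The reference period also differs by arm. Time to the first 6 mg dose is 2 + 2 = 4 weeks in Group A and 3 + 3 = 6 weeks in Group B. Including the minimum 6 mg step, it is 6 and 9 weeks. The plan does not say which span counts as initial titration.

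**What a treated reference does to a within-group change.** Illustration with assumed rates per 28 days of 10 before treatment, 7 in titration and 5 in maintenance:

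- fall from pre-treatment: 1 − 5/10 = 50%
- fall the plan would show: 1 − 5/7 = 29%

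**Precision of a between-group comparison.** The documents give no variance for seizure frequency, so differences are in SD units of a continuous (for example log) rate. Assumptions: two-sided 0.05, 80% power, normal approximation, and correlation r between baseline and on-treatment values. The formula is

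detectable difference = (1.960 + 0.842) × √(1 − r²) × √(1/n₁ + 1/n₂)

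All randomised patients contribute: √(1/30 + 1/30) = 0.258. Only patients retained at one year contribute: 30 × 0.30 = 9 and 30 × 0.70 = 21, so √(1/9 + 1/21) = 0.398.

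| Baseline adjustment | 30 v 30 | 9 v 21 |
|---|---|---|
| none | 0.72 SD | 1.12 SD |
| r = 0.5 | 0.63 SD | 0.97 SD |
| r = 0.7 | 0.52 SD | 0.80 SD |
| r = 0.8 | 0.43 SD | 0.67 SD |

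The variance of the comparison falls by r²: 25%, 49% and 64%.

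In the 9 v 21 case the groups compared are no longer the randomised groups. A baseline would not remove that selection, but it would show whether the retained patients had similar pre-treatment rates. The plan does not say whether seizure counts continue after a patient stops Fycompa, so 9 v 21 is a conditional case.

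**The case against.** A reader might infer that, without a baseline, the trial cannot measure the efficacy named in objective 2. The documents do not support that. The objective is worded as a contrast between two groups, and the Subjects and Centers section says that they are randomised. A difference in on-treatment seizure rates between randomised groups needs no baseline to be unbiased, provided that all randomised patients contribute. Regression to the mean is expected equally in both arms, so it distorts only the within-group change. Chance imbalance in pre-treatment frequency is random error that the standard error already reflects. All of this stands, and it leaves loss of precision as the cost to the between-group contrast.

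Nor do the documents show that no pre-treatment count will be taken. Diaries are reviewed at week 0, seizure frequency is assessed at each visit, and patient or caregiver reports are a named data source. A week-0 count could be recorded. What can be said is that no window is defined for it and that the analysis does not use it.

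Criterion 5 admits patients on intolerance alone, which might suggest that many have few or no seizures. Criterion 2 narrows this by requiring refractory epilepsy, although neither criterion sets a count. The plan contains no responder analysis that such patients would upset.

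Finally, the within-group wording may be a slip for between groups. If so, the missing test would be supplied, but the analysis would still use no baseline.

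**Conclusion.** The point holds in this form. The seizure analysis uses two on-drug periods, with a reference that differs in length by arm, so a change from pre-treatment cannot be estimated. The between-group objective has no matching test.

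The cost to a between-group comparison is precision: about 0.72 SD detectable at 30 v 30, against 0.63 to 0.43 SD with baseline adjustment at correlations of 0.5 to 0.8. It is about 1.12 SD if only the 9 and 21 retained patients contribute, with no defined baseline on which to check that they are comparable. These sizes rest on the assumed correlations, 80% power, two-sided 0.05 and a roughly normal (log) rate. The 50% v 29% illustration rests on invented rates and shows direction only.

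This concerns a secondary endpoint. The retention primary is unaffected. The change should be made because it is cheap and because a pre-treatment count is best taken before dosing.

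**What to change.** 1. At week 0, before the first dose, record the number of seizures of each type over a defined look-back window, for example the previous 8 weeks and at least 28 days, from the patient, the caregiver and the clinic record.
2. Report titration and maintenance rates per 28 days as change from this baseline. State where each period starts and ends, and which patients contribute at final maintenance.
3. Replace the within-group ANOVA as the test of objective 2 with a between-group, baseline-adjusted analysis. Options are ANCOVA on log rates, or a negative binomial model with a time offset and log baseline as covariate. The offset also handles titration periods of different length. State how zero counts enter any log term.
4. Limit any percent-change results to patients with at least one baseline seizure. The between-group model keeps everyone.

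The cost is one entry on the week-0 form and one covariate in a named model, with no extra visits, run-in or patients. The downside is that a retrospective count is less exact than a prospective diary, so the correlation with later rates, and hence the gain in precision, may fall towards the lower end of the range shown.
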